## Analyses:

ECG parameters will be described, in terms of values at baseline, values at each post-baseline visit. Presence of clinically significant ECG abnormalities (yes/no) will be analysed.

ECG parameters will be described, in terms of values at baseline, values at each post-baseline visit. Presence of clinically significant ECG abnormalities (yes/no) will be analysed.

Description of the following binary variables (Yes/No) were also presented:

-QTcF450 =Yes if QTcF post-dose > 450msec

 $-\Delta QTcF = Yes$  if the post-dose versus pre-dose QtcD  $\ge 60$ msec

-QT500 =Yes if the QT post-dose  $\geq$  500 msec

A data list will document individual values for any patient presenting with an abnormal clinically significant value at any time point post dose. Values will be patient ID, first and second reading, treatment, age, gender, and visit.

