3.7.2. Safety criteria

The safety criteria will include:

- Adverse and unexpected events, emergent or not, reported during the study course (frequency, severity, relationship to study drug, incidence and occurrence)
- Change of vital signs parameters (heart rate, blood pressure, body weight) from baseline values

• Physical examination: abnormalities in each system class and change from baseline

• ECG parameters: in particular, calculation of the QTcF value and comparison with the QTcF value of the ECG performed at baseline. If the QTcF is \geq 500 ms or Δ between the QTcF on treatment and the QTcF at baseline is \geq 60 ms, the treatment shall be discontinued and the corresponding ECG forwarded to Bioprojet.

- Laboratory abnormalities (e.g. AEs will be defined as laboratory test results that are outside the reference range as defined by the normal range for laboratory test and clinically signification).
- Occurrence of withdrawal symptoms (to be checked during the phone call at D59 \pm 1 and at V8 end-of-study visit (D63).

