3.7.2.1. Cardiovascular safety: vital signs and ECG

Vital signs including blood pressure, heart rate and body weight will be checked at the each visit.

ECG will be performed at each visit from the screening visit (V1) to the end of the double blind-phase (V8) or at early withdrawal visit and all visits of the open-label period. The main ECG parameters including calculation of Fridericia's corrected QTc interval (QTcF = QT/ 3 \sqrt (60/HR)) and intra individual changes in these parameters will be reported and analyzed locally. If the QTcF value is \geq 500 ms, or if the change from baseline is \geq 60 ms, (observed on two consecutive occasions, i.e. after performing a recheck a few hours later) the treatment shall be discontinued and ECGs (baseline and abnormal ECG) shall be dispatched to Bioprojet.

All ECGs will be reviewed a posteriori by a central reviewer.

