# Table 1: Study Schedule measurement in blind period

Visits	Screening V0 	VI	Inclusion V2	V3	V4	V5	V6	Endpoint V7	T1- Phone Contact	V8	Premature withdrawal 
Study day	D-28	D-14	D0 ±2	D14 ±2	D21 ±2	D28 ±2	D49 ±2	D56 ±2	D59 ±1	D63 ±2	+ 5
Informed consent	X	X*									
Narcolepsy history, Medical history and prior medications	х	X									
Physical examination, vital signs	Х	Х	Х	Х	X	Х	Х	Х		Х	Х
ECG 		х	X	Х	X	Х	X	х		Х	Х
Lab tests 		х						Х			X
Selection criteria	Х	Х	Х		ý						
Polysomnography - MSLT			X7								
MWT			Х					х			
PDSS		Х	Х	Х	Х	Х	Х	Х		Х	Х
CASS		Х	Х	Х	Х	Х	X	х		Х	Х
Ullanlinna narcolepsy scale		Х	Х				Х	Х			Х
TEA-Ch		X					X				
CGI EDS + CGI Cataplexy		х	Х				Х	Х		Х	X
Childhood Depression Inventory (CDI)		Х			Х		X			Х	Х
C-SSRS		Х	Х	Х	Х	Х	Х	Х		Х	Х
Adverse events and concomitant medications	Х	х	X	Х	X	X	Х	Х	х	Х	х
Dispensation of study drugs 			X	Х	X	X		Х			
Drug accountability				Х	X	X	Х	X		Х	X
Withdrawal symptoms questionnaire (DSM IV)									X	Х	х
Patients' global opinion 								X			Х
Sleep diary delivery	Х	Х	X	X	Х	X	X	Х			
Sleep diary retrieval 		Х	Х	Х	X	X	Х	X		Х	Х

- 1 The 4-week escalating dosage phase is followed by a 4-week stable-dose period during which the dose will be 5-, 10-, 20, or 40 mg/d of pitolisant or placebo
- 2 Complete biological examination including: Red Blood Cells, White Blood Cells (differential count, absolute value), Hemoglobin, haematocrit, Mean corpuscular volume (MCV), platelet count, quick time, sodium, potassium, chloride, creatinine, alkaline phosphatases, urea, alanine aminotransferase (ALAT), aspartate aminotransferase (ASAT), gamma glutamyl transpeptidase (GGT), total bilirubin, glucose, triglycerides, total cholesterol, βHCG (only for pubescent female). Dipstick urinalysis. A urinary drug testing (test applicable to patients from 12 years).
- 3 The premature withdrawal from the study should be followed by a visit performed within a maximum of 5 days after the last dose of study drug.
- 4 The sleep diary has to be completed every evening from V0 to V8.
- 5 The global opinion will be reported by patient if able to express himself. If not will be reported either by parents or teachers.
- 6 ECG: calculation of the QTcF value and delta of QTcF values between baseline ECG and ECGs performed at each subsequent visits.
- 7 Polysomnography-MSLT will be performed the day preceding V2, unless performed during the previous year.

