#### Analysis:

They will be described, in terms of value at baseline, value at each post-baseline visit as well as in terms of change from baseline for SBP, DBP and heart rate.

Moreover, BMI will be described by class calculated by the World Health Organization (2007): underweight: < -2SD; normal range: [-2SD; +1 SD]; Overweight:] +1SD; +2SD] and obese: > +2SD, taking into account the last post-baseline value in regard to baseline state.

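### The SAP specifies no mean change from baseline by arm for QTcF or body weight, although the protocol names both changes among its safety criteria

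*SAP*

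**What the plan says.** **Protocol, weight.** Section 3.7.2 lists among the safety criteria: "Change of vital signs parameters (heart rate, blood pressure, body weight) from baseline values".

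**Protocol, ECG.** The same section asks for "calculation of the QTcF value and comparison with the QTcF value of the ECG performed at baseline", and 3.7.2.1 adds that "intra individual changes in these parameters will be reported and analyzed locally". Section 3.3.2 places vital-sign changes and ECG with QTcF among the endpoints assessed in the pitolisant and placebo groups.

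**SAP, vital signs (4.5.4.2).** Weight and BMI are on the list of parameters. All listed parameters are described by value at baseline and at each later visit, "as well as in terms of change from baseline for SBP, DBP and heart rate". BMI is also classified against WHO standards, "taking into account the last post-baseline value in regard to baseline state".

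**SAP, ECG (4.5.4.5).** The opening paragraph repeats the protocol sentence on intra-individual changes. Footnote 6 to Table 1 also calls for "ECG: calculation of the QTcF value and delta of QTcF values between baseline ECG and ECGs performed at each subsequent visits". The analysis list then says "ECG parameters will be described, in terms of values at baseline, values at each post-baseline visit". It adds presence of clinically significant abnormalities and three Yes/No variables: QTcF above 450 ms, QT of 500 ms or more, and a change flag, worded "if the post-dose versus pre-dose QtcD" and set at 60 ms or more. SAP 4.1.5.6 derives four QTcF classes. All safety summaries are by actual treatment group (4.5.4).

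**The concern.** The SAP is the document from which the tables are programmed. Its operative ECG list names no continuous change, and its change-from-baseline list leaves out weight. A programmer who follows both lists would produce columns of raw values by visit, plus categories.

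Raw values come from children aged 6 to 17, so they carry differences in age and size, most plainly for weight. The categories are built to find extreme individuals. A modest average lengthening of QTcF, or a modest weight effect over the 8-week double-blind period, could go unshown even though the protocol lists these changes as safety criteria and the data to show them are collected.

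**Working it through.** The plan states no figure on this point, so there is none to reproduce. The check is a comparison of texts, followed by an illustration of what the missing summary would show.

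**1. Commitment against specification**

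| Item | Protocol | SAP narrative | SAP analysis list |
|---|---|---|---|
| Weight change | Named in 3.7.2 | Weight listed in 4.5.4.2 | Change for SBP, DBP and heart rate only; weight by value; BMI class against baseline |
| QTcF change | 3.7.2, 3.7.2.1 | 4.5.4.5 opening; Table 1 footnote 6 | Values by visit; flag for a change of 60 ms or more; no continuous change |

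SAP 4.1.5.1 defines change from baseline for any variable, but a definition does not schedule a table. Where the SAP wants change summarised it says so: for UNS in 4.5.3.1.2, TEA-Ch in 4.5.3.3.5, and blood pressure and heart rate in 4.5.4.2.

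**2. Can the 60 ms flag stand in for a mean change?**
Inputs: 36 placebo and 72 pitolisant (SAP 4.2). The SD of QTcF change is not in the documents; 15 and 20 ms are assumed, with normal changes and a true mean shift of 10 ms.
- P(change ≥ 60) = 1 − Φ((60 − 10)/SD). At SD 15 this is 1 − Φ(3.33) = 0.0004, and 72 × 0.00043 = 0.03 children expected. At SD 20 it is 1 − Φ(2.5) = 0.0062, and 72 × 0.0062 = 0.4 children.
- For the mean difference, SE = SD × √(1/36 + 1/72) = 0.204 × SD. The 95% half-width is 1.96 × 0.204 × SD, which is 6.0 ms at SD 15 and 8.0 ms at SD 20 (4.0 ms at SD 10).
- Power to detect 10 ms is about Φ(10/SE − 1.96): 0.90 at SD 15 and 0.69 at SD 20.

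**3. Weight**
Assumed SD of change 1, 2 or 3 kg: the half-width of the arm difference in mean change is 0.4, 0.8 or 1.2 kg. For comparison, with an assumed raw SD of 15 kg the half-width on raw values is 1.96 × 0.204 × 15 = 6.0 kg. On change it is 2.7, 1.2 or 0.85 kg if the baseline-visit correlation is 0.9, 0.98 or 0.99 (assumed).

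**4. When is change more precise than raw values?**
With equal variances at both times, the SE relative to raw values is √(2(1 − r)) for change and √(1 − r²) for ANCOVA.

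| r (assumed) | Change | ANCOVA |
|---|---|---|
| 0.4 | 1.10 | 0.92 |
| 0.5 | 1.00 | 0.87 |
| 0.6 | 0.89 | 0.80 |
| 0.7 | 0.77 | 0.71 |
| 0.8 | 0.63 | 0.60 |

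Change gains only when r exceeds 0.5. ANCOVA is no worse at any r, apart from the small cost of estimating the slope.

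**5. Can a reader subtract the column means?**
Only if the same children contribute at both visits. Even then the SD and confidence interval of the change cannot be recovered without the correlation.

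**The case against.** The strongest reply is that the SAP has not dropped these commitments. Section 4.5.4.5 repeats the sentence on intra-individual changes, Table 1 calls for a QTcF delta at each visit, and the 60 ms flag is itself an analysis of change. This stands against a reader who infers that ECG intervals are described only as values per visit: the documents do not support that. It does not fill the gap. The repeated sentence refers to local analysis, while the definition in the same section takes analysable values from the central review, and neither it nor the footnote specifies a summary.

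Second, the BMI classes are age- and sex-specific and are compared with baseline, so weight is partly covered in a way that allows for growth. That also stands, but the normal class runs from −2 SD to +1 SD (SAP 4.1.5.4), which is too coarse for 8 weeks. SAP 4.1.5.4 also needs height at the corresponding visit, while protocol 6.1.2 records height at screening only.

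Third, the shells are in a separate file (SAP 5 and 6) and may already contain change tables. A reader might infer that no mean change will be produced; the available text shows only that none is specified.

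Fourth, the precision gain depends on assumed correlations, and below 0.5 change is less precise than raw values. That is correct. The case for the tables rests first on the protocol's own commitment, not on efficiency.

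**Conclusion.** The point holds as a gap between commitment and specification. For weight, SAP 4.5.4.2 omits a change that protocol 3.7.2 names. For ECG, SAP 4.5.4.5 promises change in its narrative but specifies only visit values, abnormality status and categories.

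The consequence is moderate. Under the assumed SDs of 15 to 20 ms, a mean QTcF shift of 10 ms would be expected to trip the change flag in fewer than one child of 72, while a table of mean change would estimate the arm difference to within 6 to 8 ms. These sizes rest on assumed SDs, normality and the planned arm sizes.

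A reader might go further and say that this placebo arm is the only controlled evidence on QTcF and weight in this age group. The documents do not establish that, since much of the prior clinical section is not shown. Nor does the protocol promise a formal test against placebo for these variables. The primary analysis is unaffected.

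**What to change.** In SAP 4.5.4.5, add change from baseline by visit and arm (n, mean, SD, 95% CI) for QTcF, PR and QRS, and state that it uses the centrally reviewed values. In SAP 4.5.4.2, add body weight to the parameters summarised as change from baseline. Check the table shells first, and if such tables already exist, bring the SAP text into line with them.

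Optional: a baseline-adjusted pitolisant-placebo difference at V7, with its 95% CI and no test. This goes beyond what the protocol promises, but it does not depend on the correlation exceeding 0.5.

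The cost is a few table shells and their programming. ECG and weight are already recorded at the visits concerned and ECGs are centrally reviewed, so nothing new is collected.

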- A one–stage Futility stopping will be based on Conditional Power (CP), (probability to detect a significant result at the end of the study), given the results observed at an intermediate time. CP will be estimated through B-values and (Lan & Wittes, 1988, Lan & Zucker, 93). This analysis was planned when at least 20 patients are available, and futility threshold will be CPmin=.10 involving a slight increase of type 2 error (β =0.1/.9=.111-.10 \cong .01) (Proschan, 1999). This intermediate futility analysis does not require any type-I adjustment, this trial does not plan g rejection of the null hypothesis before its end.

This analysis was delayed sine die due to necessity of reconsideration of the sample size and a proposal of change of the main endpoint. This analysis will be conducted as soon as the sample size is definitely fixed and the main endpoint endorsed by the European regulatory authority.

Adverse events and drug safety:

 Monitoring of adverse events at each visit: investigators will assess, among other things, the severity and the relationship of each adverse event to study medication.

N.B.: hallucinations, sleep paralysis, dyssomnia and automatic behaviour, which are part of the usual associated symptoms of narcolepsy will only be considered as adverse events if the number of occurrences, or severity, is increased during the study treatment period.

- Cardiovascular safety:
 - 1. Vital sign checking at each visit including blood pressure, heart rate and body weight.
 - 2. ECG at each visit and calculation of Fridericia's corrected QTc interval

Safety

13

Protocol P11-06/ BF2.649 EudraCT number: 2013-001506-29

> $\overline{\text{(OTcF}} = \text{QT}/3\sqrt{\text{(60/HR)}}$). If the QTcF is ≥ 500 ms or if the difference between the QTcF on treatment and the QTcF at baseline is ≥ 60 ms, (observed on two consecutive occasions, i.e. after performing a recheck a few hours later) the treatment shall be discontinued and the corresponding ECG forwarded to Bioprojet.

- Mood appraisal adapted to children (CDI<16) at visits: V1, V4, V6, and V8
- Columbia-Suicide Severity Rating Scale (C-SSRS) from V1 to V8.
- Blood laboratory tests (haematology, blood chemistry), at the initial screening visit (V1), at the final treatment phase evaluation visit (V7), and for any subject who withdraws prior to treatment phase completion, within five days after the last treatment intake.

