# ECG

The following classes will be derived for **QTCF** : <= 450,] 450; 480],] 480; 500] and > 500

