## Definition:

A value is considered as analysable if a non-missing value was obtained from a Sinusal rhythm ECG from the central review (Banook).

For the description of the values at each planned post-baseline visit, in case of retest, only the first analysable one measured at the visit is taken into account.

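### The SAP's 500 ms ECG flag is written on uncorrected QT, whereas the protocol's 500 ms threshold and the SAP's two neighbouring flags are on QTcF

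*SAP*

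**What the plan says.** **Protocol threshold.** The synopsis (Safety) states the criterion on corrected QT: "If the QTcF is ≥ 500 ms or if the difference between the QTcF on treatment and the QTcF at baseline is ≥ 60 ms". Sections 3.7.2 and 3.7.2.1 repeat both limits on QTcF. When they are met, 3.7.2.1 says that "the treatment shall be discontinued and ECGs (baseline and abnormal ECG) shall be dispatched to Bioprojet". The synopsis and 3.7.2.1 require the finding to be "observed on two consecutive occasions, i.e. after performing a recheck a few hours later) the treatment shall be" stopped; section 3.7.2 gives the same limits without that confirmation. The ECG non-inclusion criterion (3.4.2, criterion 6) is also on QTcF, at 450 ms. The protocol sets no limit on raw QT.

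**SAP flags (4.5.4.5, Analyses).** There are three Yes/No variables:
- "QTcF450 =Yes if QTcF post-dose > 450msec";
- a post-dose minus pre-dose change of at least 60 ms, labelled ΔQTcF (the defining line contains an evident typing error in the variable name);
- "QT500 =Yes if the QT post-dose" at least 500 ms.

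**SAP classes (4.1.5.6, ECG).** QTcF is grouped as "<= 450,] 450; 480],] 480; 500] and > 500", so exactly 500 ms belongs to the third class.

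**Which reading is used.** Under Definition in 4.5.4.5, analysable values come from the central review, and "in case of retest, only the first analysable one measured at the visit is taken into account".

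**Departures from the protocol.** SAP 4.6 declares none from the protocol's statistical section.

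**The concern.** The three SAP flags reproduce the protocol's three QTcF limits (450, a change of 60, and 500) with matching inequality signs. Only the third changes the variable, and no reason is given. A programmer who follows the text will code raw QT; one who assumes a slip will depart from the SAP.

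A reader of the study report would naturally take a count of zero for this flag to mean that no child reached 500 ms on the protocol's scale. Coded as written, the flag cannot show that. It could also disagree with the QTcF class table in the same report. Safety is a stated main objective of this paediatric trial, so the flag should mean what a reader will take it to mean.

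**Working it through.** The plan gives no figure to reproduce. The check compares definitions, using the correction formula given in both documents.

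**Inputs**
- Formula (Protocol 3.7.2.1, SAP 4.5.4.5): QTcF = QT / (60/HR)^(1/3).
- Protocol limit: QTcF ≥ 500 ms.
- SAP flag as written: QT ≥ 500 ms.
- SAP top class: QTcF > 500 ms.
- Heart rates: the documents give no distribution. The rates below are assumptions chosen to show the range on both sides of 60 bpm.

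**Step 1: flag against limit.** The raw QT at which QTcF equals 500 is 500 × (60/HR)^(1/3). The QTcF at which the flag first reads Yes is 500 / (60/HR)^(1/3).

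| HR (bpm, assumed) | Raw QT when QTcF = 500 (ms) | QTcF when raw QT = 500 (ms) |
|---|---|---|
| 50 | 531.3 | 470.5 |
| 60 | 500.0 | 500.0 |
| 70 | 475.0 | 526.4 |
| 80 | 454.3 | 550.3 |
| 90 | 436.8 | 572.4 |
| 100 | 421.7 | 592.8 |
| 120 | 396.9 | 630.0 |

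The two criteria coincide only at 60 bpm. Above it the flag is too strict; below it, too lenient.

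**Step 2: one case each way**
- Missed: HR 90, QT 440 gives QTcF = 440 / (60/90)^(1/3) = 503.7. The protocol's number is reached, but the flag reads No.
- False: HR 50, QT 500 gives QTcF = 500 / (60/50)^(1/3) = 470.5. The protocol's number is not reached, but the flag reads Yes.

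**Step 3: classes against limit.** A QTcF of 499 falls in the third class and is below the limit, so the two agree. A QTcF of 501 falls in the top class and is above the limit, so they agree again. Only a QTcF of exactly 500 differs: it meets the limit but sits in the third class. The missed case in step 2 (503.7) is counted in the top class. A value of exactly 500 escapes both displays only when heart rate is above 60 bpm, because at or below 60 the raw QT is then at least 500 and the flag reads Yes.

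**Step 4: overlap with the change flag.** If the analysed baseline QTcF is at most 450 ms (non-inclusion criterion 6), any post-dose QTcF of 450 + 60 = 510 or more trips the change flag. With a baseline of 440 or less, any QTcF of 440 + 60 = 500 or more trips it. Only baselines above 440 combined with post-dose values from 500 to just under 510 can escape the change flag, and within that band anything above 500 is still in the top class. This relies on eligibility and analysis using similar readings; the protocol has ECGs analysed locally, while the SAP analyses central readings.

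**The case against.** The strongest reply is that little is lost. The top QTcF class counts every value above 500 ms at any heart rate. The change flag catches most of the same patients (step 4), and the 450 ms flag catches all of them. The SAP also reports maxima for continuous variables (4.1.2) and adverse events leading to withdrawal of treatment (4.5.4.1), and it plans a listing: "A data list will document individual values for any patient presenting with an abnormal clinically significant value at any time point post dose". The flag is probably a slip, given the typing error in the line above it, and nothing in the protocol obliges the SAP to tabulate the discontinuation limit.

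Most of this stands. A reader might infer from the two mismatches that no planned table counts patients at the protocol's limit, or that the report would understate QT risk. The documents do not support either reading: the top class does the counting except at exactly 500 ms, and the mock tables are a separate file that was not available, so their content cannot be asserted. Nor does the SAP rank this flag as its main QT summary.

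It is also fair to say that correcting the flag would not identify patients who met the full discontinuation rule. The synopsis and 3.7.2.1 require confirmation on a recheck, whereas the SAP describes the first analysable central reading at a visit.

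What does not stand is leaving the line alone. A probable slip in a final SAP is still the instruction that will be programmed. The listing depends on a judgement of clinical significance, not on the 500 ms limit, and it is not a count by arm.

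**Conclusion.** The flag is wrong as written and should be corrected. It applies 500 ms to uncorrected QT, where the protocol and the companion flags use QTcF. It can miss patients at or above the protocol's number when heart rate exceeds 60 bpm, and can flag patients below it when heart rate is under 60. The direction follows from the formula alone. How often either error would occur cannot be stated, because the documents give no heart rates.

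The class boundary is a minor mismatch that affects only a QTcF of exactly 500 ms. Taken together, this is an error in one planned variable, partly covered by other displays; it is not a failure to report QTcF prolongation. The conclusion covers the SAP text only, since the mock tables were not seen.

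**What to change.** 1. In SAP 4.5.4.5, replace the third flag with: QTcF500 = Yes if post-dose QTcF ≥ 500 ms. Correct the variable name in the change flag at the same time.
2. In SAP 4.1.5.6, set the QTcF classes to ≤ 450, ]450; 480], ]480; 500[ and ≥ 500.
3. State that the flag uses the first analysable, centrally reviewed reading at a visit, and that it is not a count of patients who met the two-occasion discontinuation rule.
4. Check that the mock tables carry the same definitions.

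The cost is a line or two in each of two SAP sections. No new data are needed: the protocol's schedule of events already requires QTcF to be calculated, and all ECGs are centrally reviewed. The change aligns reporting with the protocol's existing number and alters no clinical rule. Separately, protocol section 3.7.2 omits the recheck condition that the synopsis and 3.7.2.1 include; those passages must be reconciled, and no view is taken here on which is right.
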